6.6 Criteria for study termination

- (1) Reaching the study endpoints;
- (2) Any subject experiencing a life-threatening or fatal serious adverse event related to the study vaccine during the study;
- (3) The study meets the criteria for suspension ($\geq 15\%$ of subjects experience \geq Grade 3 adverse events, and these do not resolve to below Grade 3 within 48 hours), and it is determined that these events are related to the study vaccine.

If the study is terminated early, the sponsor will immediately notify the investigator, clinical trial institution, ethics committee, and regulatory authorities of the reason for termination in accordance with the relevant regulatory requirements. The investigator should report to the clinical trial institution and IRB, providing a detailed written explanation.

Regardless of the reason for suspension or termination, the investigator must immediately inform the subjects and ensure appropriate follow-up is conducted.

7. Study Evaluation and Procedures

7.1 Screening Evaluation and Procedures

The study will be conducted in accordance with all applicable regulatory requirements. Additionally, the study will comply with the Good Clinical Practice (GCP) guidelines, all relevant subject privacy requirements, and the principles of the Declaration of Helsinki. After identifying the study sites and obtaining ethics committee approval, the investigator or their authorized representative will distribute recruitment notices to subjects who meet the age, vaccination history, and health status requirements before the study begins, and contact and register these individuals, inviting them to participate in the study.

The informed consent process must be completed before any study procedures are conducted. Before enrollment, the investigator will inform the subjects about the study, and both the subject and the investigator will sign two copies of the Informed Consent Form, one for the subject and one to be retained at the study site.

The investigator will assess eligibility by conducting an inquiry based on the "Inclusion and Exclusion Criteria," obtaining information on the subject medical and vaccination history, and performing axillary temperature checks and physical examinations for all subjects, including measurements of height, weight, skin condition, and blood pressure. Women of childbearing age will undergo a urine pregnancy test. Screening information and demographic data (such as birth date, gender, and ethnicity) will be recorded in the Vaccination and Follow-up Record Book.

7.2 Immunogenicity Evaluation and Procedures

All subjects will have blood samples collected twice: once before vaccination and once 30 days after the full immunization. ELISA will be used to detect varicella-zoster virus (VZV) gE-specific antibodies, and flow cytometry will be utilized to assess the activation of VZV gE-specific CD4+/CD8+ T cells. The proportion of subjects with at least two cytokines (TNF- α , IFN- γ , IL-2, CD40L) activated will be calculated to evaluate both humoral and cellular immune responses induced by the vaccine.

7.3 Safety Evaluation and Procedures

7.3.1 Physical Examination

A physical examination will be completed during the screening period.

7.3.2 Temperature Check

Temperature checks will be conducted during the screening period and before vaccination.

7.3.3 Safety Assessment

The safety analysis cohort will include all subjects who meet the following criteria:

- Have received at least one dose of the study vaccine or control vaccine according to randomization;
- Have sufficient data for safety analysis (at least one dose and follow-up for safety);
- Have not received other prohibited medications or vaccines per protocol. For detailed information on the safety follow-up time and content, please refer to Section 5.1.9.

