5.1.10.1 Restricted Medications

At enrollment, the investigator should inquire about any medications the subject is currently using to ensure that the subject has not been taking antipyretics, analgesics, or antihistamines.

Preventive medications are those used to prevent potential solicited adverse events (AEs) that may occur during the solicitation period following vaccination. For example, if an antipyretic is taken to prevent the onset of fever when no fever is present, that antipyretic would be considered a preventive medication.

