8.3 Analysis Sets

Full Analysis Set (FAS): This includes all subjects in both the experimental vaccine group and the similar active control vaccine group who follow the intention-to-treat (ITT) principle. Subjects must have been randomized, completed vaccination, and have baseline and at least one post-immunization immunogenicity result. For subjects with vaccination number errors, immunogenicity evaluation will follow the original randomized group.

Per-Protocol Set (PPS): This set includes all subjects in the experimental and active control vaccine groups who meet inclusion/exclusion criteria, are randomized, complete vaccination, and have baseline and 30-day post-full immunization immunogenicity results. Subjects with major protocol deviations impacting immunogenicity evaluation will be excluded, though data prior to deviations may still be included in the analysis.

Safety Set (SS): This includes all subjects who received any dose of the vaccine.

Safety analyses for each dose will be based on the actual number of subjects who received each dose. Specifically: The first-dose safety set includes all randomized subjects who received the first dose of the study vaccine. The second-dose safety set includes all randomized subjects who completed the second dose of the study vaccine.

Safety analyses for each dose will follow the ASAT (All Subjects As Treated) principle, analyzing subjects based on the vaccine group they actually received.

The determination of the above analysis sets will occur in a blinded data review meeting before database lock, with input from the primary investigator, sponsor, statisticians, and data managers.

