8.5 Protocol Deviations

Protocol Deviations refer to any modifications or actions that do not follow the study
Study protocol/Version 1.1 /Date: Dec.8, 2023

protocol design or procedures without prior approval from the ethics committee. Actions that do not impact subject rights, safety, benefits, or the integrity, accuracy, and reliability of trial data, nor affect safety or primary endpoint evaluations, are considered protocol deviations. Actions that impact subject rights, safety, benefits, or the integrity, accuracy, and reliability of trial data, as well as those affecting safety or primary endpoint evaluations, are considered serious protocol deviations (protocol violations).

Examples of protocol deviations (including but not limited to):

- 1) Subjects did not sign the updated version of the informed consent form in a timely manner.
- 2) Storage and management of the study vaccine did not follow protocol requirements, or vaccine use was not confirmed as suitable before administration.
- 3) Diary cards and contact cards were not collected or distributed as required.
- 4) Other deviations.

Examples of protocol violations (including but not limited to):

- 1) Subjects entered the study without informed consent.
- 2) Subjects did not meet any inclusion criteria but were enrolled in the study.
- 3) Subjects met any exclusion criteria but were enrolled in the study.
- 4) Subjects did not receive the study vaccine according to the assigned vaccine allocation.
- 5) Vaccine dose, frequency, or administration route did not comply with protocol requirements.
- 6) Subjects used prohibited medications or those restricted by the protocol.
- 7) Subjects met withdrawal criteria but were not withdrawn from the study.
- 8) Other violations.

For protocol deviations/violations occurring during the study, site investigators must report the facts, process, cause, and impact of the event to the study responsible organization. The principal investigator or lead collaborative investigator should provide guidance on handling the event. Serious protocol deviations/violations must be reported to the ethics committee.

Researchers should provide targeted training for personnel involved in protocol violations to prevent recurrence and document the training process.

9. General Considerations: Regulatory, Ethical, and Trial Oversight

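### Sections 7.3.3 and 8.3 define the safety population incompatibly, and the 7.3.3 version excludes vaccinated subjects on post-randomization events

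*Protocol*

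**What the plan says.** Protocol 7.3.3 sets three conditions for the safety analysis cohort:

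- The first concerns dosing and allocation: "Have received at least one dose of the study vaccine or control vaccine according to randomization".
- The second concerns completeness of data: "Have sufficient data for safety analysis (at least one dose and follow-up for safety" (closing bracket omitted).
- The third concerns other products taken: "Have not received other prohibited medications or vaccines per protocol".

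Protocol 8.3 has one condition: "Safety Set (SS): This includes all subjects who received any dose of the vaccine". It adds safety sets for each dose and an as-treated rule, "analyzing subjects based on the vaccine group they actually received". It has no data condition and no medication condition.

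Three other sections bear on the third condition of 7.3.3:

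- Section 5.1.10.1 (Restricted Medications) describes a check at enrollment to "ensure that the subject has not been taking antipyretics, analgesics, or antihistamines". It then defines a post-dose category: "Preventive medications are those used to prevent potential solicited adverse events (AEs) that may occur during the solicitation period following vaccination".
- Section 5.1.10.2 (Allowed Medications) permits necessary medication when a subject has an adverse event.
- Section 8.5 lists as a protocol violation: "Subjects used prohibited medications or those restricted by the protocol". It does not say that such subjects leave the safety analysis.

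The protocol gives no explicit list of prohibited medications.

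**The concern.** Two incompatible populations serve the same five safety endpoints of Section 2.2.2, so two analysts working faithfully from the protocol could produce different safety tables. A separate analysis plan would not remove the contradiction, because it stands in the protocol itself.

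The 7.3.3 version is also the weaker one. Medication or vaccines taken after dosing, and completeness of follow-up, are post-randomization events. Excluding on them gives up the comparison of everyone vaccinated, and the result is distorted whenever exclusion is related to having an event. With no list of prohibited products, deciding who is excluded would be partly a matter of judgment.

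Tolerability against the active control is a contrast that this protocol stresses (Sections 1.1 and 3.2.1), so the denominator of the incidence tables matters.

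**Working it through.** **The definitions side by side**

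| Case | Section 7.3.3 | Section 8.3 |
|---|---|---|
| Dosed, took a preventive antipyretic, if that counts as prohibited | Out | In |
| Dosed, received another vaccine against the protocol's rules | Out | In |
| Dosed, then judged to lack safety follow-up | Out | In |
| Given the other arm's vaccine by mistake | Out, or kept under the randomized arm, depending on how the first criterion is read | In, under the vaccine received |
| Took medication to treat an adverse event | In (allowed by 5.1.10.2) | In |

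The definitions differ in the first four rows. The third also sits badly with Section 6.2.2, which uses all data up to withdrawal. The fourth conflicts with the as-treated rule on either reading.

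**How large could the effect be?** The protocol states no figure to reproduce, so this is an illustration under assumptions.

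Inputs:
- LZ901 event rate 26.85%, the Phase II high-dose rate of vaccination-related solicited reactions (Section 3.2.3.2).
- Control event rate 60% to 100%. The 100% is the Phase I adverse event rate (Section 3.2.3.1); the lower end is assumed.
- Exclusion probabilities e1 (subjects with an event) and e0 (subjects without): assumed pairs from 5%/5% to 30%/5%, and reversed at 2%/10% and 5%/20%.

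Formula: observed rate = p(1 - e1) / [p(1 - e1) + (1 - p)(1 - e0)]. The shift is the observed minus the true risk difference, LZ901 minus control.

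Exclusions in the control arm only, control rate 60%, true difference 26.85 - 60 = -33.15 points:
- e1/e0 = 30%/5%: control observed 0.42 / (0.42 + 0.38) = 52.5%; shift **+7.5 points**. Expected control exclusions: 150 × (0.6 × 0.30 + 0.4 × 0.05) = 30.
- e1/e0 = 5%/20%: control observed 0.57 / (0.57 + 0.32) = 64.0%; shift about **-4.0 points**. Expected control exclusions: 150 × (0.6 × 0.05 + 0.4 × 0.20) = 16.5.

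Same probabilities in both arms, control rate 100% (control stays at 100%), true difference 26.85 - 100 = -73.15 points:
- 30%/5%: LZ901 observed 0.18795 / (0.18795 + 0.694925) = 21.3%; shift about **-5.6 points**.
- 5%/20%: LZ901 observed 0.255075 / (0.255075 + 0.5852) = 30.4%; shift about **+3.5 points**.

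These are the extremes of the scenarios examined. With e1 = e0 the shift is exactly **zero** in every scenario.

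**The case against.** A reader might infer more than the text supports, in three ways.

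*That 7.3.3 removes subjects because they reacted to the vaccine.* Antipyretics, analgesics and antihistamines are what people take for reactions, so the inference is natural. But 5.1.10.2 allows necessary medication for an adverse event, and 7.4.2 requires it to be recorded. The sentence in 5.1.10.1 naming those drugs is an enrollment check. The post-dose category there is preventive use, illustrated by an antipyretic taken before any fever. Treating a reaction should therefore not trigger exclusion.

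*That the control arm must lose more subjects, making it look better tolerated than it is.* The Phase I rates of 100% (control) and 30% (high dose) are adverse event rates, not rates of medication use, and that section describes the events as mainly Grade 1 and needing no treatment. It would be possible to assume that 10% to 20% of an arm is dropped and that all of them had an event; a true 70% would then read (0.70 - 0.10)/0.90 = 67% or (0.70 - 0.20)/0.80 = 63%. Nothing in the protocol supports either assumption. Preventive users and recipients of other vaccines may have had fewer events, and the shift would then reverse.

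*That an excluded subject's SAE is lost.* SAEs are collected from the first dose to six months after full immunization (5.1.9), reported to the sponsor within 24 hours (7.4.4), covered in the DSUR (7.4.9) and reconciled with the pharmacovigilance database (10.2.10). Only the summary table could omit one.

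It is also fair to say that 8.3 is the formal analysis-set section, while 7.3.3 sits in a procedures chapter, so 8.3 is probably what was meant.

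These objections limit the claim about bias. They do not remove the contradiction: the text gives 8.3 no precedence, and 7.3.3 says expressly whom the safety cohort will include.

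**Conclusion.** The contradiction is established from the text alone. The sections differ on three matters: conformity with the randomized allocation, sufficiency of safety data, and use of prohibited medication or vaccines. Following 7.3.3 would exclude vaccinated subjects on post-randomization grounds, change the denominators throughout the safety tables, and possibly omit an excluded subject's SAE from the endpoint 5 summary.

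No direction or size of bias can be fixed from the protocol. The illustrative range of about -5.6 to +7.5 percentage points depends wholly on assumed exclusion probabilities and an assumed span of control event rates. It crosses zero, and it is zero if exclusion is unrelated to having an event. The any-dose set of 8.3 avoids this exclusion effect, so the passages should be reconciled before the analysis sets are determined.

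**What to change.** Replace all three criteria in 7.3.3 with a reference to the Safety Set of 8.3: any dose received, analysed as treated. The first criterion must go too, because its tie to the randomized allocation conflicts with the as-treated rule; deleting only the second and third would leave part of the contradiction. Keep the existing pointer to Section 5.1.9 for follow-up times and content.

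Report prohibited or preventive medication use, and other vaccines received, as a listing or as a sensitivity analysis on the full Safety Set.

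The cost is a few lines of protocol text. Concomitant medications and vaccines are already recorded under 5.1.10, so no new data, visits or subjects are needed.

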7.4 Adverse events and serious adverse events

7.4.1 Definitions of AE and SAE

Adverse Event (AE): Refers to any undesirable medical occurrence experienced by a subject after receiving the study drug. This can include symptoms, signs, diseases, or abnormal laboratory results, but it does not necessarily have a causal relationship with the study drug.

Serious Adverse Event (SAE): Refers to any adverse medical occurrence experienced by a subject after receiving the study drug, meeting any of the following criteria:

- 1) Results in death;
- 2) Is life-threatening, meaning the subject was at immediate risk of death at the time of the adverse event (not to be confused with potential risks of death if the condition worsens);
- 3) Results in hospitalization or prolongation of an existing hospitalization;
- 4) Results in persistent or significant disability/incapacity;
- 5) Leads to a congenital anomaly or birth defect;
- 6) Other important medical events.

Medical and scientific judgment should be used to decide whether to expedite the report of other situations. Events that may not immediately threaten life, result in death, or require hospitalization but necessitate medical intervention to prevent one of the above outcomes are also generally considered serious.

For further details on AE and SAE definitions, refer to Appendices 11.1 and 11.2.

7.4.2 Identification and Documentation of AEs and SAEs

During subject training, the importance of promptly reporting adverse events (AEs) is emphasized, and researchers should remain vigilant in identifying, investigating, and managing these events as they occur. For both solicited and unsolicited AEs experienced by subjects, the researcher should inquire whether the subject required hospitalization, outpatient treatment, or took any medications independently, and these details should be documented. Throughout the study, researchers should carefully observe the subject response to the vaccine without leading questions and encourage truthful reporting.

In the case of a serious adverse event (SAE), the investigator is responsible for reviewing all relevant documentation (e.g., hospital records, physician orders, lab reports, and diagnostic information). To clarify the nature and causality of the SAE, the

investigator may be asked by the sponsor to arrange clinical assessments/tests. If a subject is confirmed to have died during the study or follow-up period, a death certificate stating the cause of death should be obtained from the hospital.

Investigators should collect comprehensive case records as much as possible, but these should not replace study records. All information related to an SAE must be recorded in the original records, the eCRF, and the SAE report form. If medical records need to be disclosed for medical review, all personal identifiers should be redacted before release.

Investigators must establish an emergency plan for handling SAEs within the study and train all relevant personnel accordingly. Measures should be in place to promptly detect any clinically significant illnesses/events following vaccination and ensure that subjects receive appropriate care at designated hospitals in line with national regulations and current medical standards. The investigator should document the AE symptoms, onset time, severity, management, and outcome while analyzing its relationship to the study vaccine. Medications used to treat the AE should be recorded in the subject original records and eCRF.

For further details on assessing AE severity, SAE, and causality with vaccine administration, refer to Appendices 11.3 and 11.4.

7.4.3 Follow-up for AEs and SAEs

Subjects who experience adverse events (AEs) will be followed up until the event has resolved or improved, returned to baseline, or if the investigator determines that further follow-up is unnecessary, or if the subject is lost to follow-up. For AEs that lead to study termination or remain ongoing at the end of the study, the investigator should continue monitoring. Vaccine-related AEs should be followed until resolution, while unrelated events (such as illnesses) may be concluded once a physician diagnosis is obtained.

In case of disagreements or disputes during AE management, the investigator must cooperate with the sponsor to address the issue and assist the subject with medical evaluation if necessary. The sponsor has the obligation and responsibility to unconditionally ensure subject safety, providing humane care and compensation for subjects experiencing vaccine-related AEs during the study.

7.4.4 SAE Reporting

For any SAE occurring during the study, the investigator must inform the principal investigator and sponsor within 24 hours of awareness via phone, email, or online reporting. A complete written report on the Serious Adverse Event Report Form should be submitted, detailing the full description of the adverse reaction/event, onset time and type, duration, intensity, causality with vaccination, outcome, treatment (symptomatic), and other relevant clinical and laboratory data. After the initial SAE report, the investigator should continue to monitor the SAE, submitting follow-up reports with new or updated information, including any changes to the previous report and event

outcomes, focusing on unresolved/recovering SAEs until a definitive outcome is reached. For hospitalized subjects, the investigator should obtain the hospital records, which include the full progression and outcome of symptoms, all drug treatments, and detailed medical records. This information should be promptly reported as new or updated information.

The investigator should track the subject SAE outcome and aim to follow up until symptoms resolve, completing a summary report. For medically irreversible conditions, follow-up should continue until symptoms stabilize, return to pre-treatment levels, or when an alternative explanation is provided, completing the summary report.

In cases involving death, the investigator must report to the sponsor and ethics committee, providing an autopsy report (if available) and a final medical report.

7.4.5 SAE Regulatory Reporting Requirements

The investigator is responsible for promptly reporting SAEs to the sponsor (and to the ethics committee, if required) to enable the sponsor to fulfill their responsibilities. The sponsor must immediately analyze and assess all SAEs reported by the investigator, including evaluating their severity, causality with the study vaccine, and whether the event was anticipated. Any SAE identified by the sponsor as a suspected unexpected serious adverse reaction (SUSAR) must be promptly reported to all participating investigators, study sites, ethics committees, and the National Medical Products Administration's Center for Drug Evaluation (CDE) within seven days, with follow-up information provided within the subsequent eight days. If the sponsor and investigator cannot reach an agreement on the causality assessment between the adverse event and the vaccine, a prompt report should still be made if either party deems it impossible to rule out a connection with the study vaccine.

